11. MEASUREMENT OF EFFECT

Although the clinical benefit of combination ipilimumab and decitabine has not yet been established, the intent of offering this treatment is to provide a possible therapeutic benefit, and thus the patient will be carefully monitored for tumor response and symptom relief in addition to safety and tolerability. Patients with MDS/AML will be assessed by standard criteria. For the purposes of this study, patients should be re-evaluated at the end of cycles 1, 2 and 4, and then every 3 cycles on treatment, and then at time of suspected relapse if relevant. The aspirate sample collected at the end of cycle 1 is for correlative research only. In addition to a baseline PET scan (for those with extramedullary disease, not required for those with leukemia cutis only), follow-up response scans will also be obtained at the end of four cycles of combination therapy following initial documentation of an objective response.

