- There will be three phases: priming, induction and maintenance
- Hydroxyurea may be used to control leukocytosis
- **Lead In: Priming phase with decitabine alone**
 - **Treatment:** Decitabine 20 mg/m² IV daily over 60 minutes (+/- 15 minutes) x 5 consecutive doses on **days 1-5** given per institutional guidelines
 - **Pre-medication prior to chemotherapy:** per institutional standards
 - Supportive medication such as allopurinol or equivalent should be considered in patients with white blood cell counts $> 10 \times 10^9 / L$ to reduce risk of tumor lysis syndrome.
 - Clinic visits on day 1 and day 15 (+/- 3 days)
 - Labs on day 1 and day 15 (+/- 3 days)
 - Research blood and aspirate collection at the end of the lead in period on a day between days 24-28 (see correlative calendar in [section 10.2](#)).
 - Adverse event evaluation:
 - **Intolerability during priming phase:** If a patient experiences unexpected intolerance to decitabine during the lead in that cannot be ameliorated by supportive care measures, then that patient will not continue on trial and will be replaced.
 - **Graft versus host disease (GVHD):** If there is evidence of acute GVHD that requires the use of systemic corticosteroids agents during the lead in, then the patient will be taken off study due to concern for safety with checkpoint blockade and replaced.
- **Cycles 1-4: Induction phase with combination decitabine and ipilimumab**
 - **Pre-Treatment Requirements**
 - Hematologic criteria to start cycle 1: None required
 - Hematologic criteria to start cycle 2:
 - If there is persistent disease (e.g. peripheral blasts, any marrow disease, persistent leukemia cutis or other form of extramedullary disease) at the time of disease response evaluation at the end of cycle 1, then there are no hematologic requirements to start cycle.
 - In the absence of disease, patients must have an absolute neutrophil count $\geq 500 \times 10^9 / L$ or platelet count to $\geq 25,000 \times 10^9 / L$ to proceed; otherwise administration of treatment will be delayed.
 - Hematologic criteria to start cycle 3:
 - If there is persistent disease (e.g. peripheral blasts, any marrow disease, persistent leukemia cutis or other form of extramedullary disease) at the time of disease response evaluation at the end of cycle 2, then there are no hematologic requirements to start cycle.

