 - In the absence of disease, patients must have an absolute neutrophil count $\geq 500 \times 10^9 / L$ or platelet count to $\geq 25,000 \times 10^9 / L$ to proceed.
 - Hematologic criteria to start cycle 4:
 - If there is persistent disease (e.g. peripheral blasts, any marrow disease, persistent leukemia cutis or other form of extramedullary

disease), then there are no hematologic requirements to start cycle .

- In the absence of disease, patients must have an absolute neutrophil count $\geq 500 \times 10^9/L$ or platelet count to $\geq 25,000 \times 10^9/L$ to proceed; otherwise administration of treatment will be delayed.

- **Treatment**

- Decitabine 20 mg/m² IV daily over 60 minutes (+/- 15 minutes) x 5 consecutive doses on **days 1-5** every 4 weeks given per institutional guidelines
 - **Pre-medication prior to chemotherapy:** per institutional standards
- Ipilimumab IV (per dose level as in table above) on **day 1** over 90 minutes (+/- 15 minutes) every 4 weeks for a total of 4 doses during induction
 - Dose escalation levels: 3 mg/kg (**starting dose**, dose level 0), 5 mg/kg (dose level 1), and 10 mg/kg (dose level 2)
 - Dose de-escalation level: 1 mg/kg
- Decitabine will be dosed prior to ipilimumab on day 1
- Vitals signs will be repeated hourly from time of ipilimumab infusion for up to two hours after infusion ends (+/- 30 minutes) on day 1 after first dose and up to one hour after infusion ends (+/- 30 minutes) on day 1 for subsequent doses.

- Clinic visits (including physical exam, medication review, ECOG and AE review)
 - Cycle 1: on day 1 and day 15 (+/- 3 days)
 - Cycles 2-4: on day 1 (+/- 3 days).

- **Procedures:**

- Labs
 - Cycle 1: on day 1, day 15 (+/- 3 days).
 - Cycles 2-4: on day 1 (+/- 3 days).
 - End of cycles 1, 2 and 4 on day of bone marrow biopsy (on a day between days 24-28).
- Bone marrow biopsy (including aspirate (if aspirable), core, flow cytometry, cytogenetics) will be at the end of cycles 1, 2 and 4 (on a day between days 24-28) for response assessment.
- If sole extramedullary disease (unless leukemia cutis), routine evaluation may include PET imaging (if FDG avid at time of diagnosis) at the end of cycles 2 and 4 (on a day between days 24-28) for response assessment.

- **Correlative studies:** peripheral blood and aspirate collection at the end of cycles 1, 2 and 4 on a day between days 24-28 (see correlative calendar in [section 10.2](#)).

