- i: For bone marrow biopsies, the minimum requested includes (1) aspirate (if aspirable), (2) core, (3) flow cytometry (if sufficient blasts; may not be possible in setting of low blasts or remission; if MRD flow cytometry is an option we will accept this data in lieu of standard flow cytometry if this test is available at the time of suspected remission), (4) cytogenetics if possible, (5) molecular testing per institutional guidelines (suggested at minimum at time of screening and relapse but not required; correlatives will include genotyping leukemic blasts). Core biopsy is mandatory at screening, at the end of cycles 2 and 4- See sample collection table in section 10.2 for details. If a diagnostic bone marrow biopsy was performed within 4 weeks of treatment start and no anti-leukemic therapy has been given (except for hydrea and radiation), then flow cytometry and cytogenetics do not need to be repeated. If a diagnostic bone marrow was performed within 2 weeks of treatment start, then only a research aspirate and research core are required to be collected during screening. In cases of persistent leukemic blood, bone marrow biopsy can be performed on day 1 of subsequent cycle prior to treatment.
- j: Aspirate ONLY for correlative study (unless inaspirable). See Correlative studies.
- k: For those with leukemia cutis only - repeat evaluation at end of cycles 1, 2 and/or 4 (pending response)- If there is suspected resolution or response based on skin exam, biopsy may occur sooner as clinically indicated. After confirmation of resolution of lesion, there does not need to be a repeat biopsy at the same site. If there is concern for persistence of disease based on skin examination, then repeat biopsy is recommended at the end of cycles 1, 2 and/or 4 if it can be safely performed.
- l: Routine response evaluation for patients in Arm A who are status post allo-HCT only. Peripheral blood source only. Can be performed locally and if not available locally then should be analyzed at site where patient's transplant was performed.
- m: For those with known HBV they should get an HBV viral load (PCR). For those with known HCV they should get an HCV viral load (PCR). It is recommended that patients with known HBV get monthly (+/- 14 days) HBV viral load assessments after ipilimumab is initiated. Please update overall PI if there is significant or clinical concern for HBV re-activation despite anti-viral therapy.

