⁹Bone Marrow Core: At the screening time point, submission of bone marrow biopsy core will be mandatory (to be fixed in 10% buffered formalin prior to sending using materials provided in kit) (this extra core should be collected at time of screening marrow for the purpose of IHC correlative studies). Mandatory submission of bone marrow biopsy core or 6-8 unstained slides will be collected at the end of cycles 1, 2 and 4. For the end of treatment/suspected relapse timepoint, a core is requested, but not mandatory. At the EOT/suspected relapse timepoint, 6-8 unstained slides may be sent in lieu of a fresh core sample. Cores arriving in formalin will be transferred to 70% ethanol and decalcified in the Brigham & Women's Hospital Pathology Core laboratory in preparation for staining with IHC in the [name] Laboratory. These bone marrow core samples should be shipped Monday-Thursday at room temperature. Archival tissue (FFPE) from participants who are consented on the clinical trial including bone marrow biopsies (tissue blocks or slides) performed at other time points where a bone marrow is clinically indicated (while on study) may be requested at a later time for IHC analysis in the [name] laboratory

¹⁰ PB sample for PD studies: It is preferred that the PB is drawn at one visit. However, depending on scenario, the peripheral blood PD sample can be collected over two visits if clinically necessary (e.g. for the "screening/pre-treatment" collection, PB can be collected at screening up until day 1 of lead-in cycle as long as it's prior to decitabine dosing; for the "end of cycle 2" collection, PB can be collected on days 24-28 of cycle 2 up until day 1 of cycle 3 as long as it's prior to decitabine and ipilimumab dosing). If this is the case, please update the study team to anticipate and plan on two sample deliveries.

¹¹Germline assessment: Skin biopsies will be performed on patients who are identified to be exceptional responders (at any point of the trial) and some non-responders (in dose expansion cohort) after discussion with the overall PI. Samples are to be sent in normal saline in appropriate leakproof container to BWH CAMD by way of Dana-Farber. If sent from outside of DFCI, the sample should be sent frozen (both saline and tissue) and shipped to the Pasquarello Tissue Bank at Dana-Farber Cancer Institute. DNA will be extracted in batches in Brigham and Women's Hospital CAMD. This is optional.

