APPENDIX D ACUTE MYELOID LEUKEMIA RESPONSE CRITERIA

Cheson, B et al., J Clin Oncol, 2003, 4642-9.

Morphological Complete Remission (CR):

-Normalization of the peripheral blood absolute neutrophil count $> 1.0 \times 10^9/L$, platelets $>$ than $100 \times 10^9/L$ no residual evidence of extramedullary disease and bone marrow aspirate with $\leq 5\%$ blasts, no blasts with Auer rods

Morphological Complete Remission with incomplete blood count recovery (CRi):

-Same as CR but without normalization of the peripheral blood absolute neutrophil and platelet count

Relapse from CR or CRi:

-Reappearance of leukemic blasts in the peripheral blood; or $> 5\%$ blasts in the bone marrow not attributable to another cause (e.g. recovery of normal cells following treatment-induced aplasia or use of growth factors) OR
-Appearance or reappearance of extramedullary disease.
-If there are no circulating blasts and no extramedullary disease and the bone marrow blast percentage is $> 5\%$ but $< 20\%$, then a repeat bone marrow performed at least 7 days after the first marrow examination and documenting bone marrow blast percentage $> 5\%$ is necessary to establish relapse.

Partial Remission (PR):

-Normalization of the peripheral blood absolute neutrophil count $1.0 \times 10^9/L$, platelets $>$ than $100 \times 10^9/L$, and at least a 50% decrease in the percentage of marrow aspirate blasts to 5-25%, or marrow blasts $< 5\%$ with Auer rods.

Cytogenetic Responses

Complete cytogenetic response: An abnormal clone is detected in all metaphases prior to treatment and only normal metaphases are observed in all metaphases following treatment.

Partial cytogenetic response: An abnormal clone is detected in all metaphases prior to treatment and the post-treatment sample has 50% or fewer abnormal metaphases compared to the pretreatment value.

Cytogenetic non-response: An abnormal clone is detected in all metaphases prior to treatment and neither complete nor partial cytogenetic response is observed in post-treatment specimens. Specimens with normal cytogenetic results before treatment will not be evaluated for cytogenetic response. The method used to determine cytogenetic response will be standard metaphase cytogenetics.

Stable disease:

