-Subjects who fail to achieve CR, CRi, or PR and who do not have criteria for PD will be defined as having the stable disease. If the subject dies prior to response assessment at the end of Cycle 1, then they will be classified as "indeterminate".

Progressive disease (PD): may be defined as ONE of the following:

- >50% increase in peripheral blood or bone marrow blasts from best assessment with minimum threshold of 20% blasts in the marrow or $1.0 \times 10^9/L$ blasts in peripheral blood.
- Development of biopsy proven extramedullary leukemia (if the subject has extramedullary disease at baseline, then PD will be defined by blood and marrow criteria or if new sites of extramedullary disease appear).
- If subject who present with an initial marrow blast percentage sufficiently high to preclude the ability to base disease progression on a >50% increase in marrow blast percentage, disease progression should be based on peripheral blood criteria or development of extramedullary leukemia as above.

Persistent Disease

Hematologic Persistence – Bone marrow or peripheral blasts >5% after d+30 following alloSCT

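### Section 11 makes the end-of-cycle-1 aspirate research only, while the rest of the plan uses that marrow to assess response, so marrow-based response and progression dates can differ by about 28 days between sites

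*Combined protocol and SAP*

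**What the plan says.** Section 11 contains two adjacent statements that do not fit together. The first says that "patients should be re-evaluated at the end of cycles 1, 2 and 4, and then every 3 cycles on treatment". The next says: "The aspirate sample collected at the end of cycle 1 is for correlative research only".

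Elsewhere the end-of-cycle-1 marrow is treated as a clinical evaluation:

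- Section 5.1, induction procedures: the marrow, with aspirate, core, flow cytometry and cytogenetics, "will be at the end of cycles 1, 2 and 4 (on a day between days 24-28) for response assessment".
- Section 5.1, hematologic criteria to start cycle 2: the rule depends on whether disease persists "at the time of disease response evaluation at the end of cycle 1".
- Section 11.1: biopsy and aspirate are taken at the end of cycles 1, 2 and 4, with cytogenetics and flow cytometry at each evaluation.
- Section 10.1 calendar: the cycle 1 day 24 marrow carries footnote i, the full work-up. Only the end-of-lead-in marrow carries footnote j, which limits it to a correlative aspirate. Footnote 7 in Section 10.2 likewise makes the lead-in aspirate research only.
- Appendix D: an AML patient is classed as indeterminate "If the subject dies prior to response assessment at the end of Cycle 1".

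Appendix D also defines AML complete remission through "no residual evidence of extramedullary disease and bone marrow aspirate with" a blast threshold, and partial remission through the fall in aspirate blasts.

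**The concern.** A site that takes the Section 11 sentence at face value has no clinical blast count from the cycle 1 aspirate. It cannot record AML CR, CRi or PR from that marrow, and it may not record marrow progression either. A site that follows Section 5.1 can do both. The same patient could then receive different dates, and occasionally a different best response, depending on where treatment was given.

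The endpoints exposed are secondary: best overall response, PFS and duration of response. There is also a limited link to the DLT data. Section 5.1 takes patients who progress at a response assessment off study unless they are benefiting, and a cycle 1 assessment falls about halfway through the 56-day window. With at most 24 patients per arm, and three to six per dose level, one patient handled differently is visible in the results.

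**Working it through.** No stated figure in the plan is in dispute. The check is a comparison of texts, followed by short arithmetic on size.

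**1. Can the passages be read together?** The most natural harmless reading is that the sentence refers only to the extra tube drawn for research. That reading does not explain the wording. The Section 10.2 table also requests research aspirates at the end of cycles 2 and 4, so singling out cycle 1 would serve no purpose. The passages conflict, and the research-only sentence is the outlier. It may have been carried over from the lead-in aspirate, but that is inference.

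**2. Timing of the first marrow evaluation.** Inputs are a 28-day lead-in, 28-day cycles, and a marrow on days 24-28 of the cycle (Section 5.1). Counting from lead-in day 1, without delays:

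- End of cycle 1: 28 + 24 = 52 to 28 + 28 = 56.
- End of cycle 2: 28 + 28 + 24 = 80 to 28 + 28 + 28 = 84.
- Difference: 80 − 52 = 84 − 56 = 28 days.

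PFS runs from registration rather than lead-in day 1, but the 28-day difference does not depend on the origin.

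**3. Share of the DLT window.** The window is 56 days from cycle 1 day 1 (Section 5.2). A patient removed at the end of cycle 1 has been observed for about 28/56 = 50% of it. A patient who continues can be observed for all of it.

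**4. Effect of one patient on the response rate.** Section 13.1 foresees 6 + 6 = 12 or 6 + 12 = 18 patients at the MTD/RP2D and gives 90% exact intervals within ±25% and ±21%. Exact (Clopper-Pearson) intervals reproduce this as the maximum half-width:

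| n | widest case | 90% interval | half-width |
|---|---|---|---|
| 12 | 6/12 | 24.5% to 75.5% | 25.5 points |
| 18 | 9/18 | 29.1% to 70.9% | 20.9 points |

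One patient reclassified moves the rate by 1/12 = 8.3 points or 1/18 = 5.6 points.

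**5. Who can be affected?** Dates move only when the cycle 1 marrow is the first evidence of the change. Best response differs only in narrower cases:

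- The patient responds in the cycle 1 marrow and has lost the response, or has no marrow, by the end of cycle 2.
- The patient is called progressive at cycle 1, which closes the best-response period in Section 11.1 before a delayed response is counted.

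The documents give no rate for any of these, so the number affected cannot be computed.

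**The case against.** The strongest reply is that this is a single stray sentence. To follow it, a site must disregard the sentence before it, Section 11.1, Section 5.1 and the calendar. It also names the aspirate, not the whole procedure. Much of that stands, and it limits how often the conflict would bite. It does not say which text governs, and the stray sentence sits in the section that defines how effect is measured.

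A reader might infer more than the documents support:

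- **That all early dates shift.** AML progression under Appendix H can also rest on peripheral blasts or new extramedullary disease. MDS hematologic improvement needs no marrow, and the MDS criteria in Appendix E refer to bone marrow rather than specifically to aspirate. OS is untouched.
- **That evaluability becomes site-dependent.** Section 13.5 makes anyone with one ipilimumab dose evaluable for response. Section 13.1 makes a cycle 1 progressor evaluable for DLT after 28 days, which the disputed marrow on days 24-28 barely precedes. The amount of follow-up may differ; evaluability largely does not.
- **That the start of cycle 2 generally turns on this marrow.** Footnote b in Section 10.1 waives final marrow results when persistent disease is evident or counts meet the criteria. What remains is mainly patients with low counts and no other evidence of disease.
- **That an extra ipilimumab dose necessarily precedes detection of marrow progression.** Section 11.1 calls for an unscheduled marrow on clinical concern, and Section 5.1 lets benefiting patients continue after progression with approval. The hematologic DLT criterion is read at the end of the window.
- **That the core-biopsy footnotes show the same conflict.** Footnote i says "Core biopsy is mandatory at screening, at the end of cycles 2 and 4", while footnote 9 in Section 10.2 says "Mandatory submission of bone marrow biopsy core or 6-8 unstained slides will be collected at the end of cycles 1, 2 and 4". These mainly govern research samples. Footnote i already lists a core in its minimum for every marrow, and the Section 10.2 table asks for marrow-core slides at cycle 1. This is at most a minor alignment.

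**Conclusion.** The inconsistency is real and unresolved in the current text, and the Section 11 sentence is wrong as written against the rest of the plan. It should be corrected, but it does not undermine the primary objective. For patients whose status is first determined by the cycle 1 marrow, response and progression dates, and hence PFS and response duration, can differ by about 28 days between sites. A few patients could differ in best response or in how much of the DLT window is observed.

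This assumes 28-day cycles without delay and that some site acts on the research-only sentence. The one-patient effect of 8.3 or 5.6 points illustrates scale; it is not an estimate of bias, because neither the number nor the direction of reclassifications can be derived from the documents.

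**What to change.** Delete the research-only sentence in Section 11, or limit it to the end-of-lead-in aspirate, which footnote j in Section 10.1 and footnote 7 in Section 10.2 already make research only. Section 11 would then agree with Sections 5.1 and 11.1 that the end-of-cycle-1 marrow counts for response and for dating progression as an endpoint.

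For the start of cycle 2 and for removal on progression, the request is only that Section 11 be reconciled with the Section 5.1 criteria and footnote b in Section 10.1. Which clinical rule applies is for the sponsor to state.

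Optionally, align the research-sample wording on the cycle 1 core or slides between footnote i, the Section 10.2 table and footnote 9.

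The cost is an amendment to wording. The cycle 1 aspirate, core, flow cytometry and cytogenetics are already scheduled, so no procedure or patient is added.

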11.1 Antitumor Effect – Hematologic Tumors

Please see [Appendix D](#) for IWG Response Criteria for AML [6]. Disease progression will be determined by European LeukemiaNet 2017 criteria (Appendix H).

Please see [Appendix E](#) for IWG Response Criteria for MDS [7].

Bone marrow biopsy and aspirate will be performed at screening (will serve as baseline) and end of cycles 1, 2 and 4, and every 3 cycles thereafter (end of cycles 7 and 10). If there is evidence or clinical concern for disease progression, then a bone marrow biopsy and aspirate will be

collected. At each evaluation the patient should have aspirate (if aspirable), cytogenetics and flow cytometry performed. Genotyping will be performed as a part of study correlates.

Hematologic evaluations will be performed with CBC with differential at a minimum of once per cycle. Response assessments may be determined by labs (CBC with differential, particularly platelet count and absolute neutrophil count) within 2 weeks of a bone marrow biopsy as long as it is obtained prior to day 1 of the next cycle.

The best overall response is the best response recorded from the start of the treatment until disease progression/recurrence.

- For those with AML: Best overall response including CR and CRI will be recorded. Patients may remain on study if they have evidence of clinical benefit, stable disease, partial remission, complete remission or complete remission with incomplete count recovery.
- For those with MDS: Best overall response rate will include CR, marrow CR, PR, and hematologic improvement.

